## 5.2. Research procedures:

**Screening:** see section 19

**Randomization:** The parent(s) who consent to participate in the study will be randomized using a 2x2 computerized block randomization ([www.sealedenvelope.com/simple-randomiser/v1/lists](http://www.sealedenvelope.com/simple-randomiser/v1/lists)). Participants will be stratified by NICU into two groups A) usual care B) yoga intervention. At the time of consent, the study coordinator will be **blinded to the randomization**, and the parent will be presented with a sealed envelope that identifies group A (control) and group B (intervention).

When both parents from the same family are eligible and interested in study participation, both will be consented and then randomized to the same group and followed separately with outcome surveys. Since parental outcomes are likely correlated. Prior to randomization we will ask parents to designate one parent as the primary study participant. Outcomes of the parent designated as the secondary study participant will be included in exploratory analyses that appropriately accounts for potentially correlated outcomes.

**Intervention Group:** Parents will receive an information sheet (see 'Welcome Packet YOGA GROUP' in "other attachments" ) explaining the practice of yoga, meditation and breathing exercises, FAQs about the study including how to access an electronic tablet while in the unit (if parent is unable to supply their own device), instructions on how to access study website and Zoom. Parents will also sign the study consent form and HIPAA authorization, receive a personal yoga mat, ear-pods (if needed), and details regarding compensation for the study (see 23.1). Participants have the opportunity to keep the ear-pods and yoga mat at the conclusion of the study. Parents in the intervention group will receive usual care for parent support offered in site NICU and be enrolled in a 6-week virtual yoga curriculum (see description in 5.1). They will also be asked to periodically fill out questionnaires throughout the study.

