## 10. Number of Subjects

- 10.1. Total number of subjects to be enrolled locally:

At least 20 parents of NICU inpatients, 20 NICU inpatients

- 10.2. Total number of subjects to be enrolled across all participating sites:

20 parents (and potentially their partners) randomized to control group (10 from UWMC and 10 from SCH)

20 parents (and potentially their partners) randomized to intervention group (10 from UWMC and 10 from SCH)

- 10.3. Number of screened subjects versus the actual number enrolled in the research:

All infants at UWMC and SCH NICU will be screened if born <32-weeks gestation and/or <1500g or LOS estimated >6 weeks

- 10.4. Power analysis:

According to research by Pace et al. (2016) the proportion of parents with low birthweight infants hospitalized in NICUs who endorsed anxiety approached 50%. Smaller studies of parents of very low birthweight infants have shown rates of depression in mothers and fathers ranging from 30-60% (Meyer, EC et al (1994), Davis, L (2003), Mackley, AB, 2010). The study population in Aim 1 (NICU parents) reported a higher level of baseline anxiety and stress (~60%) regarding having an infant in the NICU.

Based on this information, and an anticipated 20-30% decrease in stress and anxiety with yoga practice, we will need a sample size of 16 parents enrolled in each group to see a power of 0.80 at an alpha level of 0.05. Given this information, and the possibility of attrition of study participants, we will plan to enroll 20 parents in control and 20 parents in intervention group for this pilot study.

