## 19. Recruitment Methods

19.1. When, where, and how potential subjects will be recruited:

**University of Washington and Seattle Children's Hospital:** All infants born <32 weeks gestation and/or <1500g or with a length of stay estimated to be >6 weeks, and who has been admitted to the University of Washington NICU or Seattle Children's NICU will be screened for eligibility by principal investigator ([name]).

A screening form (see other attachments) will be maintained on REDCap to document patients screened, reasons for eligibility/ineligibility, reasons for nonparticipation of eligible parents. A recruitment log (see other attachments) will be maintained in a password protected database located on the Seattle Children's server containing MRN of enrolled infant, record ID of parent participant and date of consent for data collection purposes. PI will send secure email with names of patients who meet inclusion criteria to weekly attending of record for final approval to contact (re: patient/parent stability). PI or representative (resident/fellow or APP caring for infant) will make first contact with parent with a standardized bedside conversation or phone

call to explain study. If family is interested in more information PI will meet family in person in the NICU at least 10 days after admission. Following consent, the introductory survey and first set of self-report scales will be completed during enrollment process.

Participants in the intervention group will be guided on how to log into the study website, and will be instructed to respond to emails with links for self-report scales to be completed throughout the study period. Participants in the control group will be instructed to respond to emails with links for self-report scales to be completed throughout the study period. The first week of intervention will begin on the Monday after enrollment or 10-14 days after infant admission to the NICU.

Note that UWMC is a birth hospital, thus 10 days after admission will likely be 10 days of life. Infants are typically referred/transferred to SCH NICU from other NICUs, and thus 10 days after admission may reflect different ages. The inclusion criteria for both institutions will be the same.

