20.2. Plan for documenting consent/assent/permission:

Consent will be documented in writing on a paper form provided at the time of the consent conversation. REDCap screening form will document date of consent. REDCap randomization form will record date of randomization and outcome of randomization (Group A or B).

20.2.1. Plan to confirm that the individual who provides the electronic signature is the subject (or their parent/LAR), when the signature is not personally witnessed by a member of the study team or explanation as to why such a plan is unnecessary:

Study coordinator will only receive actual signatures of participants on paper consenting forms. NO electronic signature will be used.

20.2.2. If using electronic consent, plan to manage consent documentation over the life of the study in a way that maintains integrity and accessibility:

N/A

20.2.3. If consent/permission will be documented in writing (check one):

"SOP: Written Documentation of Consent (HRP-091)" will be followed.

"SOP: Written Documentation of Consent (HRP-091)" will not be followed.

Process of documenting consent:

N/A

20.2.4. If consent/permission will not be documented in writing (check all that apply, *complete Section 21.13 to request a Waiver of Documentation of Consent*)

- A written statement/information sheet describing the research will be provided to subjects.
- A written statement/information sheet describing the research will not be provided to subjects. Explain: N/A
- A consent script will be used.

20.3. Waiting period available between approach and obtaining consent/assent/permission:  
N/A

20.4. Process to ensure ongoing consent/assent/permission:  
N/A

20.5. If this box is checked, "SOP: Informed Consent Process for Research (HRP-090)" will be followed:

20.6. If "SOP: Informed Consent Process for Research (HRP-090)" will not be followed, address the following:

20.6.1. Role of the individuals listed in the application as being involved in the consent process:  
N/A

20.6.2. Time that will be devoted to the consent discussion:  
N/A

20.6.3. Steps that will be taken to minimize the possibility of coercion or undue influence:  
N/A

20.6.4. Steps that will be taken to ensure the subject's understanding:  
N/A

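### If the 2x2 site-stratified blocks are short and fixed, the sealed envelopes conceal allocation only in part; the arm may also be known before baseline self-report

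*Protocol*

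**What the plan says.** Section 5.2 allocates consenting parents by a "2x2 computerized block randomization", and continues: "Participants will be stratified by NICU into two groups A) usual care B) yoga intervention". It says that the study coordinator is blinded to the randomization at the time of consent, and that "the parent will be presented with a sealed envelope that identifies group A (control) and group B (intervention"). It does not give a block length, does not say whether the length varies, and does not name who generates or holds the list.

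Section 10.2 sets the stratum size: "20 parents (and potentially their partners) randomized to control group (10 from UWMC and 10 from SCH"), and the same for the intervention group. That is 20 parents per site, 1:1.

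On recruitment, Section 19.1 has the PI screen, the PI or a representative make first contact, and then "PI will meet family in person in the NICU at least 10 days after admission". Section 20.1 has the research coordinator or an investigator seek consent. Section 19.1 places the introductory survey and the first self-report scales after consent, during enrolment.

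On what becomes known afterwards, Section 19.1 states: "Participants in the intervention group will be guided on how to log into the study website". Section 20.2 states: "REDCap randomization form will record date of randomization and outcome of randomization (Group A or B"). Section 16.1 has the PI review self-report data from both arms every week. Section 5.2 lets the coordinator stand in for the instructor at the Zoom check-ins, which are offered to intervention parents only.

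**The concern.** An envelope hides the next card. It cannot hide an assignment that can be worked out from the cards already opened. In an open trial with short fixed blocks in each site, anyone who remembers the recent allocations at that site sometimes knows the next one and often has a good guess. The blinding in Section 5.2 applies at the moment of consent. Nothing in the protocol blinds the same staff to earlier assignments.

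The stake is selection bias. Someone who expects the next arm to be yoga could, without meaning to, approach a keener or less distressed parent first. Outcomes are unblinded self-report and the target is 20 parents per arm, so a few such choices could move the effect estimates that Section 5.1 wants for planning a definitive trial.

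A second route to bias needs no prediction. If the envelope is opened at consent and the first DASS21 and PSS:NICU are completed afterwards, baseline answers may be coloured by knowing the arm. Those scores would then be a poor reference for measuring change.

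**Working it through.** The protocol gives no predictability figure, so there is nothing to reproduce.

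**Inputs.** Two arms, 1:1, stratified by NICU (Section 5.2); 20 parents per site and 40 in total (Section 10.2). Block length is an assumption, shown over a range. The recruiter is assumed to know every earlier allocation at the site and the block length or, for mixed blocks, the possible lengths.

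**Formulas**, for a fixed block with *m* per arm:
- Share known with certainty (one arm already used up in the block): 1/(m + 1).
- Share guessed correctly by always naming the arm that is behind: 1/2 + [2^(2m−1)/C(2m, m) − 1/2]/(2m).

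**Block of 4 by position (m = 2).** Position 1 is a coin toss, 1/2. At position 2 the arm behind holds 2 of the 3 remaining places, 2/3. At position 3, with probability 1/3 the first two matched and the rest is certain; otherwise it is a coin toss: 1/3 + 2/3 × 1/2 = 2/3. Position 4 is always certain, 1.
- Correct guesses: (1/2 + 2/3 + 2/3 + 1)/4 = 70.8%.
- Certain: (1/3 + 1)/4 = 33.3%, or 6.7 of 20 at each site.

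| Blocks within site | Certain | Of 40 | Guessed correctly | Of 40 |
|---|---|---|---|---|
| Fixed 2 | 50.0% | 20 | 75.0% | 30 |
| Fixed 4 | 33.3% | 13.3 | 70.8% | 28.3 |
| Fixed 10 | 16.7% | 6.7 | 65.3% | 26.1 |
| One block of 20 | 9.1% | 3.6 | 61.7% | 24.7 |
| Random mix of 4 and 6 | 5.8% | 2.3 | 68.5% | 27.4 |

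The last row comes from simulated 20-parent lists with a recruiter who knows that both sizes are in use. Chance alone gives 20 correct of 40.

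**Room to choose.** Section 24.2 reports 10–20 qualifying admissions a month at UWMC and 5–14 at SCH, with 5 months of recruitment. That is 50–100 and 25–70 infants for 20 places at each site, before refusals and exclusions. Who is approached first is therefore a real choice.

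**Timing of the envelope.** Section 5.2 presents it at the time of consent. Section 19.1 puts the first scales after consent. No section requires the scales to be saved before the envelope is opened.

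**The case against.** The strongest reply is that the block length is unknown. The sentence after 2x2 describes two groups and stratification by NICU, so the phrase may mean no more than that. A protocol may properly withhold block length from the staff who read it, so the silence is not an error. If each site had one block of 20, only 9.1% of assignments would be certain. This stands, and it makes the predictability figures conditional.

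The protocol also contains safeguards. All infants meeting the criteria are screened, reasons for ineligibility and nonparticipation are logged, and the attending approves contact (Section 19.1). Consent from day 10 with participation by day 14 (Sections 5.1 and 20.1) leaves little room to delay a family. These limit steering but do not remove it: the attending judges stability rather than order of approach, and a log records choices without preventing them.

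A reader might infer three stronger things that the document does not support:
- That the blocks are small and fixed. This is one reading of an ambiguous phrase.
- That the recruiting staff hand over the envelope and enter the arm. Those sentences name no actor. That staff learn past allocations rests instead on the PI's weekly review of both arms, the coordinator's possible role in the Zoom sessions, and the website onboarding.
- That the envelopes give no protection. Even with fixed blocks of 4, two thirds of assignments stay uncertain.

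**Conclusion.** The point holds conditionally. If 2x2 means a fixed block of 4 per site, a recruiter who tracks allocations knows 33% of assignments in advance and can guess 71%. For a fixed block of 2 the figures are 50% and 75%. Concealment by envelope is then incomplete. This rests on two assumptions: that the blocks are short and fixed, and that recruiters follow the running allocations, which the protocol gives them the means to do. It does not show that steering will occur.

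The order of envelope and baseline scales is a separate weakness that does not depend on block length. The stated sequence allows a parent to know the arm before giving baseline scores, although the text does not say that this will always happen.

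**What to change.** For parents not yet randomised:

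1. Use permuted blocks of randomly varying size within each NICU, for example 4 and 6, and withhold the sizes from recruiting staff. Replace the 2x2 wording with text that gives the strata and ratio without revealing block size.
2. Have the list generated and held by someone who does not recruit. ITHS, already named in Section 14.1 for statistical help, could do this, or the list could sit in REDCap, which is already in use.
3. Reveal the arm only after consent and the baseline scales are saved.
4. Keep running arm totals by site from those who choose and approach families, as far as an open trial allows.

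Step 1 alone is not enough. Against fixed blocks of 4 it lowers certain assignments from 33% to about 6%, but correct guesses only from 71% to about 68.5%. If the existing list already uses long or varying blocks, step 1 adds little, and steps 2 to 4 are the part to make.

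The cost is one new list and a change in the order of enrolment steps. The statistical downside is an arm difference of up to 3 per site if a block of 6 is left incomplete; at exactly 20 parents the difference must be even, so at most 2 (11 against 9). Section 9.2.1 describes this text as a modification of an existing approval, and Section 24.2 starts enrolment in August 2021, so parents may already be randomised. In that case, leave their allocations alone, start the new list for later parents, and record the date of the switch. The last block of the old list may then also stay incomplete.

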### SELF-REPORT SURVEYS:

*Yoga in the NICU Introduction Survey:* demographic survey completed on a smart device at the time of enrollment. This survey (see supplemental materials) will include basic demographic data including age, ethnic background, race, education level, employment status, assessment of household food insecurity (measure of SES), assessment of prior mental health treatment (in the past 12 months before delivery of premature baby), assessment of yoga practice prior to and during pregnancy (for either birth parent or participating partner). We will also collect a personal email address where subsequent study surveys will be sent directly from REDCap.

To further assess parental stress, anxiety and depression, participants in both arms of the study will complete the following surveys (see supplemental materials)

1. *Depression, Anxiety, Stress Scale (DASS21)*: to assess baseline participant depression, anxiety, and stress with these three self-report scales. Each of the three scales contains 7 items divided into subscales with similar content (depression, anxiety, and stress). Scores for depression, anxiety and stress are calculated by summing the scores for relevant items.
  - Two-times: at enrollment and conclusion of study
2. *Parental Stress Scale: Neonatal Intensive Care Unit (PSS:NICU)* a 26-item self-report scale designed to measure the degree of stress experienced by parents during hospitalization related to alterations in their parental role, the appearance and behavior of their child, and sights and sound of the unit.
  - Three times: at study start, midpoint (3 weeks) and at the conclusion of the study
3. *Postpartum Bonding Questionnaire (PBQ)* a 19-item self-report scale evaluating two factors involved in parent-infant bonding.
  - One time: at conclusion of the study
4. *Course Completion Survey* filled out by all participants at the conclusion of the study. There will be specific questions in this survey directed through branching logic to parents in the intervention group relating to safety and adverse events as well as parent opinions about the yoga intervention.

To address the baseline level of **post-partum depression** in the parent population, we will obtain individual responses and composite scores of *Edinburgh Postnatal Depression Scales (EPDS)* that have been administered by the unit Social Worker (as a regular part of parental NICU care). EPDS are entered by SW and stored in the infant EPIC chart (at UWMC) or the maternal chart (at SCH) (see section 5.4). For non-birth parent participants, or those participants who have not received a baseline EPDS by the unit social worker, the study coordinator will administer the EPDS (see other attachments) at the time of enrollment as part of this research study. The EPDS has been validated for use in male partners (Matthey S, et. al. *Journal of Affective Disorders* (2001)). In the circumstance that birth parent declines participation and non-birth parent consents to participation, we will not obtain birth parent EPDS scale.

**Video and Web-based Resources:** A study website will be designed using the [www.rise.com](http://www.rise.com) (team url = nest) platform, a secure, user friendly, and engaging virtual platform for creating courses, guides and training content. Rise is easy to navigate, adaptable for all devices (mobile, tablet, PC), and supports multimedia activities. Study website will be designed to accommodate the 6-week study period (see webpage screen shots in supplemental materials). Yoga sessions (30 min each) will be pre-recorded and uploaded as links on the study website (see sample files in supplemental materials). A tablet device will be made available for use in the building (UWMC/SCH) for those parents who do not have a suitable personal device.

- UWMC: 9 tablets available for parents to borrow courtesy of NICU
- SCH: 3 tablets have been made available for parents to borrow courtesy of Child Health, Behavior and Development (CHBD) and Seattle Children's IT

Parental response and adherence to the online program will be assessed throughout the study period by tracking participation of the yoga sessions on the website (rise.com)

**Zoom check-ins:** There will be optional weekly virtual (Zoom) 'check-in sessions' available for

participants in the intervention group to speak directly with a yoga instructor in real time to ask questions. A recurring date/time will be selected by study coordinator, and yoga instructors will sign up to host sessions using a google document available in a shared drive. The study coordinator will substitute if a yoga instructor is unavailable, and relay questions from participants to the instructor via email. For Spanish speaking participants logging into the zoom session, we will call a Certified Language Interpreter (CLI) remotely (see other documents for CLI access) to interpret Q&A session.

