## 5. Procedures Involved

### 5.1. Study design:

This will be a randomized controlled pilot study to elucidate the optimal research strategy with which to implement mind and body interventions for **parents** of NICU patients, at 2 sites (University of Washington NICU and Seattle Children's Hospital NICU) comparing: 1) control group 2) yoga intervention (i.e: breathing exercises + meditation +postures).

Parents will be enrolled in the study after day 10 of infant admission to NICU and begin participation by day 14 of NICU admission (see Recruitment methods section 19).

The non-birth parent will be invited to participate in this study and may participate without the birth parent. If both parents are participating the partner would be randomized to the same group (control or intervention) see randomization section 5.2. In the circumstance that the birth parent declines participation and non-birth parent consents to participation, we will still obtain consent from parents to access infant medical records, however we will not obtain birth parent EPDS scale (see section 5.2)

If an infant is transferred from UWMC to SCH as part of their clinical care, a parent enrolled initially at UWMC may continue participation in this study while infant is admitted at SCH.

**Control group:** Parents will experience usual care including all available parental support as practiced in the specific site NICU. We will utilize a 'waitlist' control model for this project, whereby the parents randomized to control group will have unlimited access to the online platform hosting the yoga intervention following the completion of the study period.

**Intervention group:** In addition to usual care, the parents randomized to the intervention group will be provided a yoga mat and participate in 30-min online led yoga sessions done at least twice weekly at the parent's pace using a secure, virtual platform (website). There will be 6 total yoga classes (one introduced per week for a 6 week period). Each yoga session will be divided into three components, which will vary in duration based on a curriculum designed *specifically* with the post-partum state of mothers in mind:

- **Yoga postures (Asana)** = low impact gentle postures meant to be done individually
- **Breathing techniques (Pranayama)** = deliberate modifications of breath such as rapid

- diaphragmatic breathing, slow/deep breathing, alternate nostril breathing, breath holding

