**Control Group:** Parents will sign the study consent and HIPAA forms. Information will be provided regarding the waitlist control model (see 5.1), and details about the compensation for the study (see 23.1). Parents in the control group will receive usual care for parent support offered in site NICU. They will also be asked to periodically via email to fill out identical questionnaires as the intervention group throughout the 6-week study period.

In general, a participating non-birth parent may skip self-report items that are considered not applicable, however there should be very few items that cannot be answered by either parent.

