**16. Provisions to Monitor Data to Ensure the Safety of Subjects**

16.1. Plan to periodically evaluate the data collected regarding both harms and benefits to determine whether subjects remain safe:

Principal Investigator [name] will evaluate self-report data collected in both arms of the study weekly, and report to clinical social worker at specific NICU site regarding any individual parent with concerning symptoms of depression, anxiety or stress that may not have previously been identified.

16.2. Data reviewed to ensure safety of subjects:

Depression, Anxiety, and Stress Scale (DASS21), Parental Stressor Scale: NICU (PSS:NICU), Postpartum Bonding Questionnaire (PBQ).

16.3. Safety information collection procedures:

Individual REDCap surveys will be assigned directly to parents via email. Data will be stored in a longitudinal secure REDCap database.

16.4. Frequency of cumulative data review:

weekly

16.5. Conditions that trigger an immediate suspension of the research:

N/A

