## 22. Payments/Costs to Subjects

- 22.1. Amount, method, and timing of payments to subjects:

Parents participating in both control and intervention groups will receive a total of \$50 in gift cards (tango cards) during the course of the study:

- \$20 after completing 1 week of intervention, Intro survey, DASS21, first PSS:NICU.
- \$10 after completing 3 weeks of intervention and second PSS:NICU
- \$20 after completing 6 weeks of intervention, second DASS21, third PSS:NICU, PBQ, course completion survey

Distribution of tango cards will be done via email by the study coordinator and tracked in both a REDCap form and an excel sheet using participant randomization number and record ID (see other attachments)

Each family or pair of participants (partners) may receive only one set of gift cards totaling \$50. This will be made clear in the study consent form and parent information sheets.

- 22.2. Reimbursement provided to subjects:

- 22.3. Additional costs that subjects may be responsible for because of participation in the research:

Free WiFi is available for participants if logging into the study website from UWMC, SCH, Hotel Nexus, or the Ronald McDonald house. Study coordinators are unable to determine if free WiFi will be available if participants log into the study website from another location not listed above.

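### Solicited adverse-event questions go only to the yoga arm and only once, at study end, and the survey that holds them is missing from the section 16.2 list of safety data

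*Protocol*

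**What the plan says.** Protocol section 5.2 (self-report surveys, item 4) describes a Course Completion Survey "filled out by all participants at the conclusion of the study". Within it, certain questions are "directed through branching logic to parents in the intervention group relating to safety and adverse events"; the same branch carries opinions about the yoga. Section 22.1 fixes the timing: the last gift card is paid "after completing 6 weeks of intervention, second DASS21, third PSS:NICU, PBQ, course completion survey".

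Section 5.2 also says that control parents will "fill out identical questionnaires as the intervention group throughout the 6-week study period".

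Section 12.1 acknowledges a minimal risk of physical injury in the yoga arm, while section 3.2 enters safety endpoints as not applicable. Section 16.1 has the principal investigator look at self-report data from both arms every week. Section 16.2 names the data used for safety: "Depression, Anxiety, and Stress Scale (DASS21), Parental Stressor Scale: NICU (PSS:NICU), Postpartum Bonding Questionnaire (PBQ". The Course Completion Survey is not on that list.

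Two other channels are open during the six weeks. One is an optional weekly Zoom check-in for the yoga arm (sections 5.2 and 17.2); the other is email between participant and principal investigator (section 17.1).

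**The concern.** The protocol asks about adverse events and also sets up a weekly safety review, but as written the two do not connect. The questions reach one arm, once, after the programme is over, in a survey that the review list omits.

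Two things are at stake. First, if yoga parents report new physical complaints, no control answers exist to set beside them. Many of these parents are recently post-partum (section 19.1 notes that at UWMC ten days after admission will usually be ten days of life), so some complaints unrelated to yoga are foreseeable. Answers never requested from controls cannot be recovered at analysis, so this is a data-collection matter that a statistical analysis plan could not repair. Second, no scheduled question can pick up a physical event while that parent is still practising. A parent who stops early may never reach the survey at all.

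The pilot is meant to inform a multicenter trial (section 1.1), and 22% of surveyed hospital stakeholders had safety concerns (section 2.2). Harms data that can be interpreted would be a useful product.

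**Working it through.** The protocol gives no adverse-event rate and no precision target for safety, so there is no planned figure to reproduce. The check is mainly a comparison of what is collected, from whom and when.

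**Scheduled instruments after enrolment (sections 5.2, 16.2, 22.1)**

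| Instrument | Arms | When | In 16.2 list | Described content |
|---|---|---|---|---|
| DASS21 | both | enrolment, end | yes | depression, anxiety, stress |
| PSS:NICU | both | start, week 3, end | yes | NICU-related parental stress |
| PBQ | both | end | yes | parent-infant bonding |
| Course Completion Survey, safety questions | yoga only | end | no | safety and adverse events |

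Three things follow.

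1. Psychological symptoms have a comparator, and PSS:NICU gives one scheduled reading between baseline and end.
2. None of the three listed scales is described as asking about physical injury.
3. The only questions that could solicit a physical event are in the last row, which has no control arm, no mid-study reading and no place in 16.2.

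**Planned exposure before the first solicited question.** Section 5.1 has yoga parents "participate in 30-min online led yoga sessions done at least twice weekly" for 6 weeks.

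- At study end: 2 × 6 = 12 sessions at least; 12 × 30 = 360 minutes.
- If an item were added to the week-3 survey: 2 × 3 = 6 sessions; 6 × 30 = 180 minutes.

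**What a two-arm comparison could show.** Section 10.2 plans "20 parents (and potentially their partners) randomized to intervention group" and "20 parents (and potentially their partners) randomized to control group". Count the 20 primary parents per arm, assume all of them answer, and assume the same event rate p in each arm. The approximate 95% half-width for the risk difference is 1.96 × √(2p(1−p)/20).

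- p = 10%: 1.96 × √(0.18/20) = 0.186, about ±19 points.
- p = 30%: 1.96 × √(0.42/20) = 0.284, about ±28 points.

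Both rates are assumptions; the protocol gives none. The normal approximation is rough at this size, and attrition would widen the intervals. As the protocol stands, no between-arm difference in solicited adverse events can be estimated at all.

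**The case against.** The strongest case on the other side has five parts.

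- **Harm is monitored in both arms.** This stands for psychological harm. A reader might infer that no harm of any kind has a comparator or is seen before week 6. The documents do not support that, because the symptom scales go to both arms, are named as safety data, and include a week-3 reading.
- **Injuries can surface earlier.** This stands in part. A reader might infer that the Zoom check-in is the sole early route, but section 17.1 also provides email to the principal investigator. Both routes are voluntary, however, and the protocol does not say that reports made there are recorded as adverse events. The check-ins are for the yoga arm only.
- **Section 16.1 may already cover the survey.** It speaks of self-report data from both arms, and section 5.2 places the survey under its self-report heading. So 16.1 and 16.2 leave an ambiguity rather than a settled exclusion. With rolling enrolment, early completers' answers would also arrive while later parents are still practising. That helps later parents, not the parent who was hurt.
- **The item wording is not shown.** If the branched questions ask only about injury during yoga, controls could not answer them and background complaints would not be counted. This stands. A reader might infer that background complaints will be mistaken for yoga harm at some particular rate. That needs both an event rate and an item wording that the protocol does not give.
- **This is a minimal-risk pilot.** Section 24.2 says so, section 5.1 sets its goals as engagement, effect sizes and variability, and section 12.5 adds injury-prevention instructions. That limits the weight of the point. It does not explain why the survey that asks about adverse events should be left out of the safety list.

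The conflict with the statement that controls complete identical questionnaires is also weak. The survey description openly qualifies it, and opinions about the yoga have to be branched.

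**Conclusion.** The point holds for solicited adverse events, and in particular for physical injury. The protocol asks about them in one arm only and at one time only, after at least 12 planned sessions, through a survey that section 16.2 does not list. Under those rules a solicited physical event has no control-arm counterpart, and no scheduled question can detect it while the parent is still practising.

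The defect is structural and has no error rate attached to it. Repairing it would buy modest information: a descriptive contrast with the half-widths shown above, not a test of whether yoga causes harm. The conclusion rests on the protocol's description of the surveys, since the instruments themselves are not in the text. This is an inexpensive improvement worth making in a minimal-risk pilot; it is not a threat to the efficacy comparison.

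**What to change.** 1. In the Course Completion Survey, ask both arms the same neutrally worded item on any new injury or new physical symptom during the study period. Keep branching only for whether the parent attributes it to the yoga and for opinions about the programme.
2. Send the same item to both arms with the existing week-3 PSS:NICU. The first solicited report would then follow about 6 planned sessions rather than 12, and some parents who later stop would already have been asked.
3. Add the item to the section 16.2 list, and reconcile 16.1, 16.2 and the two survey descriptions in 5.2 so that it is clear what each arm is asked and what is reviewed weekly.
4. State that the between-arm comparison will be reported as descriptive only.

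The cost is about a minute of parent time, a REDCap edit and an IRB modification. No change to the yoga programme or to parents' care is involved.
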